Research Objectives

The objectives of this study :

Exploring the Effects of Cognitive Behavioral Therapy on Disorders of Esophageal Brain-Gut Axis Dysregulation.

Hypothesis:

- (1) Patients with disorders of esophageal brain-gut axis dysregulation often experience esophageal symptoms due to visceral hypersensitivity and esophageal hypervigilance, which can negatively affect their physical and mental health, sleep, and quality of life. Cognitive Behavioral Therapy (CBT) can help alleviate these symptoms and reduce their impact.
- (2) CBT has been shown to improve symptoms across different subtypes of disorders involving esophageal brain-gut axis dysregulation.

8. Research Methods, Procedures, and Execution Progress

1. Please describe in detail the research methods adopted in this project and the reasons for choosing them.
2. Potential challenges and solutions expected during the project.
3. If this is a continuous project, please also attach the progress report from the previous year or primary data.

Research Method

Participant

This project is a multi -center study. we will recruit cases from three medical centers in Taiwan, We plan to enroll a total of 120 participants, including 40 from our hospital, 40 from Kaohsiung Medical University Hospital, and 40 from E-Da Hospital.

This study is expected to last for 2 years, with the study period ending on December 31, 2025. We intend to recruit participants with esophageal symptoms related to disorders of the gut-brain axis communication from the Gastroenterology outpatient clinics.

Inclusion criteria for participants :

1. Age between 18 and 75 years, with clear consciousness and willingness to sign the informed consent form.

[figure not shown]
Version Date : (Version 8, 11/19/2024)

2. Participants with chronic esophageal symptoms related to esophageal-brain-gut axis communication disorders (such as heartburn, acid reflux, sensation of a foreign body in the throat, difficulty swallowing, chest pain, and chest tightness).

Exclusion criteria for participants :

1. Esophageal stricture, or a history of esophageal, gastrointestinal, or throat surgery.
2. Structural esophageal diseases (e.g., diverticula, esophageal rings), infectious esophagitis, erosive esophagitis, eosinophilic esophagitis.
3. Non-erosive gastroesophageal reflux disease or significant esophageal motility disorders.
4. A history or current diagnosis of esophageal, gastrointestinal, or other organ malignancies.

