5. Significant endocrine or rheumatic autoimmune diseases that may affect gastrointestinal motility.
6. Continuous use of medications that may affect esophageal motility (e.g., anticholinergics, morphine-like drugs, nitrates, calcium channel blockers) within the past month.
7. Use of antidepressants, selective serotonin reuptake inhibitors, or other psychiatric medications within the past three months.
8. Pregnant or breastfeeding women.
9. Individuals with mental disorders or those unable to cooperate.
10. Known allergy to tricyclic antidepressants.
11. Known allergy to selective serotonin reuptake inhibitors.
12. Known allergy to any component of proton pump inhibitors.

Research Design Flowchart

Steps to Follow

In this study, All participants will undergo questionnaire assessments and heart rate variability measurements before treatment. The questionnaires include the Gastroesophageal Reflux Disease Questionnaire (GERDQ), PROMIS GERD, DSI & GSS, RSI, Brief Esophageal Dysphagia Questionnaire (BEDQ), Esophageal Hypervigilance and Anxiety Scale (EHAS), Visceral Sensitivity Index (VSI), Sleep and Mental Health Questionnaires (Sleep Habits Questionnaire PSQI, Taiwanese Depression Questionnaire TDQ, State-Trait Anxiety Inventory STAI, Functional Dyspepsia (FD) Questionnaire, Irritable Bowel Syndrome (IBS) Questionnaire, Quality of Life Questionnaire SF-12, and Northwest Esophageal Quality of Life Scale (NEQOL). Heart rate variability will be measured using the non-invasive "Mind Technology" biofeedback system (Taiwan FDA Medical Device Certification No. 011374).

Following this, a single-blind trial will be conducted with computer-generated random allocation. Participants will receive either 6 weeks of Cognitive Behavioral Therapy (CBT) or 6 weeks of lifestyle management (sham control), with one 1-hour session per week. After 6 weeks of counseling, participants will undergo a final questionnaire assessment and heart rate variability measurement after the 12th week of enrollment. The questionnaires and measurements will take approximately 20 to 30 minutes to complete, marking the end of the trial.

Cognitive Behavioral Therapy (CBT) will be carried out according to the following steps :

(1) Education and Initial Follow-up

Version Date : (Version 8, 11/19/2024)

- (2) Heart Rate Variability and Breathing Introduction
- (3) Cognitive Restructuring and Breathing Application
- (4) Cognitive Diffusion and Behavioral Experiments

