- (5) Problem-Solving and Emotion-Focused Coping Strategies
- (6) End of Treatment and Relapse Prevention

Lifestyle Management (Sham Control) will be carried out according to the following steps :

- (1) Education and Initial Follow-up
- (2) Dietary Habits: What, When, Where, Why
- (3) Changing My Diet: Strategies and Barriers
- (4) Lifestyle Factors: Alcohol, Smoking, and Sugar
- (5) Lifestyle Factors: Sleep and Exercise
- (6) End of Treatment and Relapse Prevention

In this study, we will use non-invasive physiological signal sensors connected to a biofeedback system to measure the participants' physiological signals, including electrocardiogram (ECG) and breathing. Before measurement, participants will first apply ECG electrodes for a two-lead ECG measurement, which will then be converted into heart rate variability (HRV) indicators. Simultaneously, a non-invasive breathing sensor will be used to measure the respiratory rate per minute. Except for a very small number of participants who may experience allergic reactions to the ECG electrodes, the likelihood of side effects is less than 1%.

Multicenter Communication and Coordination Method

The hospital directors of the participating institutions and the principal investigator, [name], will communicate and coordinate via email and a Line group established for the project. The research data collected by each center will be managed and stored by the respective center's director. The hospital directors will assist in consolidating the research data from their institution, and the electronic data will be coded for identification. After the data is compiled, it will be sent back to the principal investigator. Additionally, the research physicians and staff at each participating center will have regular video conferences (every 2 months) to discuss and report on the progress of the study.

Statistical Analysis

All data will undergo normality testing using the Kolmogorov-Smirnov test. If continuous variables follow a normal distribution, they will be expressed as means and standard deviations; if not, they will be presented as medians and interquartile ranges.

For categorical variables, the Chi-square test or Fisher's exact test will be used for analysis. Continuous variables that are normally distributed will be analyzed using the unpaired t-test, while non-normally distributed continuous variables will be analyzed using the Mann-Whitney U test.

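### A Kolmogorov-Smirnov test on the trial's own data picks the between-arm test and effect measure for each continuous outcome, and neither candidate test uses the baseline score

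*Protocol*

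**What the plan says.** Protocol, section 8, Statistical Analysis: "All data will undergo normality testing using the Kolmogorov-Smirnov test". The outcome of that test governs two things.

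- **The summary:** mean and SD if the variable passes, and "if not, they will be presented as medians and interquartile ranges".
- **The two-arm test:** "Continuous variables that are normally distributed will be analyzed using the unpaired t-test", whereas "non-normally distributed continuous variables will be analyzed using the Mann-Whitney U test".

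The same switch is repeated for comparisons of more groups (ANOVA or Kruskal-Wallis). No continuous outcome is exempt. No between-arm effect measure or confidence interval is named.

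On measurement, section 8, Steps to Follow, says "All participants will undergo questionnaire assessments and heart rate variability measurements before treatment", and after the six-week programme "participants will undergo a final questionnaire assessment and heart rate variability measurement after the 12th week of enrollment". Each scale therefore has a baseline and a follow-up value. The text does not say whether the final score or the change enters the test.

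On size, section 8, Participant: "We plan to enroll a total of 120 participants". The allocation ratio is not given.

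**The concern.** There are two separate points.

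**The gate.** The method for each outcome is settled by the same data that the method will then analyse. The protocol also leaves open what decides the gate: arms tested separately or pooled, the Kolmogorov-Smirnov statistic with or without the Lilliefors correction for an estimated mean and SD, and final or change scores. Over a dozen questionnaires plus heart rate variability pass through it, so related scales in one report may end up with different tests and different summaries. A mean difference on one scale cannot be set beside a rank comparison on another. The gate is also unnecessary: with about 60 per arm, a comparison of means does not need normally distributed raw scores.

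**The missing baseline.** Neither two-arm test, as written, has a baseline term. Feeding in a change score is not ruled out, but that subtracts the baseline without adjusting for it. Precision that the collected data would supply is given up.

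**Working it through.** The protocol gives 120 with no effect size, SD or power, so there is no stated figure to reproduce. The gate's existence follows from the text alone. The calculations below only size its consequences.

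**Inputs.** From the protocol: 120 participants, two arms, significance at 0.05, baseline and week-12 values. Assumed, because the protocol gives none: 1:1 allocation (60 per arm), two-sided testing, gamma-distributed scores with skewness 1.0 to 2.0 (or normal), and baseline correlation r = 0.3, 0.5 or 0.7.

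**1. Which test is chosen.** Critical values of the statistic D: uncorrected 0.1723 (n = 60) and 0.1225 (n = 120); Lilliefors 0.114 and 0.0814. Share of outcomes sent to Mann-Whitney, uncorrected v Lilliefors (with arms separate, either arm failing is enough):

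| Skewness | Arms separate | Pooled | Pooled, arms 0.5 SD apart | Change scores, arms separate |
|---|---|---|---|---|
| 1.0 | 5% v 67-73% | 12% v 74-78% | 8% v 65-68% | under 1% v 20-26% |
| 1.4 | 23% v 93-95% | 49% v 97-98% | 34% v 91-93% | 1-2% v 41-55% |

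In the first three columns the range reflects two ways of obtaining the Lilliefors critical value (tabulated and simulated). Independent simulations gave closely similar figures.

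**2. Splits within one trial.** Thirteen scales were taken from Steps to Follow, leaving out the functional dyspepsia and irritable bowel questionnaires and heart rate variability, with inter-scale correlation 0.3-0.7. Share of trials in which the scales divide between the two tests, arms separate, uncorrected v Lilliefors:

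- normal: 0.3% v 70-74%
- skewness 1.0: 43-49% v 93-99%
- skewness 1.4: 90-96% v 42-47%
- skewness 2.0: 83-95% v under 1%

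The normal Lilliefors figure can be checked by hand. Each scale fails with probability 0.098, so for independent scales 1 - (1 - 0.098)^13 = 0.74.

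**3. Whether the route matters.** With a 0.5 SD difference, the t-test and Mann-Whitney reach opposite verdicts at 0.05 in 5-6% (normal), 8-9% (skewness 1.0) and 13% (1.4) of trials. With identical arms the gated rule rejects in 4.6-5.6% of trials (4.3-5.0% in a second simulation), and the plain t-test in 4.9-5.3%. There is no inflation, and the t-test needs no gate to hold its level.

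**4. Baseline.** In units of the outcome SD, the analysis SD is 1 for final scores, sqrt(2(1 - r)) for change scores and sqrt(1 - r²) for ANCOVA. Confidence-interval width ratios:

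- ANCOVA to final score, sqrt(1 - r²): 0.954 / 0.866 / 0.714, so 5 / 13 / 29% narrower.
- ANCOVA to change score, sqrt((1 + r)/2): 0.806 / 0.866 / 0.922, so 19 / 13 / 8% narrower.

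Power for 0.5 SD by normal approximation: the standard error at SD 1 is sqrt(2/60) = 0.1826, so power = Φ(0.5/(0.1826 × analysis SD) - 1.96). For the final score, Φ(2.739 - 1.96) = 78%. For ANCOVA at r = 0.5, Φ(3.162 - 1.96) = 89%.

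| Normal data, r = 0.3 / 0.5 / 0.7 | Approximation | Simulation |
|---|---|---|
| Final score | 78 / 78 / 78% | 77 / 78 / 77% |
| Change score | 64 / 78 / 94% | 62 / 78 / 94% |
| ANCOVA (robust SE in simulation) | 82 / 89 / 97% | 79 / 88 / 96% |

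**5. Skewed data, r = 0.5, 0.5 SD (simulated power).**

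| Skewness | t-test | Mann-Whitney | Gated rule | Change, t-test | ANCOVA | Rank ANCOVA |
|---|---|---|---|---|---|---|
| 1.0 | 78% | 84% | 78-83% | 76% | 86% | 90% |
| 1.4 | 78% | 89% | 81-89% | 75% | 86% | 95% |

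**The case against.** The best defence is that the rule is written in advance and applied mechanically, that it does not inflate type I error, and that scales with different distributions may fairly be described differently. Covariates, final or change scoring and the version of the normality test are details a protocol may leave to a statistical analysis plan. The protocol also names only per-group summaries, so effect measure here means the switch between comparing means and comparing ranks.

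Part of this stands. There is no error-rate harm, and the gate costs no power relative to a fixed t-test; against a fixed Mann-Whitney on skewed data it costs a little (78-83% v 84% at skewness 1.0). The baseline point is about efficiency. The routing and split percentages rest on assumed distributions and span almost the whole range from 0 to 100%, so they show sensitivity to unstated choices and do not predict this trial.

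It does not remove the concern. A rule that hands the choice of test to the trial data is a stated decision, which a later plan would have to reverse, not fill in. Writing the rule down does not fix the method for any outcome, and the rule itself is incomplete.

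The remedy also has a real cost on skewed, weakly correlated scores. At skewness 1.4 and r = 0.3-0.5, ANCOVA on means has 79-87% power, against 89-90% for Mann-Whitney and 81-89% for the gated rule. At skewness 1.0 and r = 0.3 it has 78-79%, against 83% and about 81% (Lilliefors gate). At skewness 1.4 and r = 0.7 it is ahead of Mann-Whitney, 95% v 89%.

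**Conclusion.** The concern holds. As written, no continuous outcome has a between-arm test or effect measure settled before the data are seen, and neither candidate test adjusts for a baseline that is measured on everyone. The first point needs no assumption. Its size does: with skewness 1.0 and 60 per arm, the unstated version of the normality test alone moves the share of rank tests from 5% to 67-73% (arms separate), and the two tests disagree on significance in 5-13% of trials when the arms differ by 0.5 SD. The second point costs 5-29% in confidence-interval width against final scores and 8-19% against change scores, for assumed correlations of 0.3-0.7. The power gain comes from using the baseline, not from dropping the gate. This should be changed, but it does not threaten the validity of the significance level.

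**What to change.** Replace the normality rule for the between-arm comparison with one named method, for example:

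> Each continuous outcome at week 12 will be compared between arms by ANCOVA adjusted for its baseline value and reported as an adjusted mean difference with a robust 95% confidence interval. ANCOVA on ranks, adjusted for baseline rank, is the sensitivity analysis. Normality tests will not decide the between-arm analysis; medians and interquartile ranges are descriptive only.

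The cost is analysis wording: no new data, visits or participants. It should be made before outcome data are examined. The price is the loss of power on clearly skewed scores with weak to moderate baseline correlation set out above. The rank ANCOVA covers that case, with 91-96% power at skewness 1.4 and correlation 0.3-0.5. If the investigators expect most scales to be strongly skewed, another single method fixed in advance would also cure the gate.

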For comparisons involving more than three groups, if the data are normally distributed, an ANOVA with post hoc tests will be conducted. If the data are non-normally distributed, the Kruskal-Wallis test will be applied. A p-value of less than 0.05 will be considered statistically significant.

Statistical analyses will be performed using SPSS 19 for Windows (SPSS, Inc., Chicago, IL, USA).

Clinical Significance and Originality of This Study

1. The originality of this study lies in its use of visceral sensitivity, mind-body connection, esophageal hypersensitivity, anxiety questionnaires, and functional gastrointestinal questionnaires to explore the effects of neuromodulators on diseases related to esophageal-brain-gut axis communication abnormalities. Patients with such conditions often experience more severe esophageal symptoms due to excessive visceral sensitivity and esophageal hypersensitivity.
2. This study aims to establish a model for Cognitive Behavioral Therapy (CBT) in disorders of esophageal brain-gut axis dysregulation. Our research examines the role of CBT in esophageal brain-gut axis dysregulation and refractory gastroesophageal reflux disease (GERD). The results obtained from this study will deepen our understanding of the pathophysiological mechanisms of esophageal brain-gut axis dysregulation and refractory GERD. The findings will help elucidate the etiology of refractory GERD, particularly when patients with GERD also present with esophageal brain-gut axis dysregulation, which leads to a lowered threshold for esophageal symptom perception. This condition can be reversed and improved through the aforementioned treatments. Furthermore, it will assist in early clinical intervention for patients with brain-gut axis communication disorders, enabling the establishment of personalized treatment strategies and the achievement of precision medicine for such patients.

9.Expected Work Items and Specific Outcomes

- (1) Please list the expected tasks to be completed within the execution period.
- (2) Expected contributions to academic research and other applied areas.
- (3) Expected training that participants will receive.

(1) Work items expected to be completed.

In this study, we will also explore the effects of Cognitive Behavioral Therapy (CBT) on disorders of esophageal brain-gut axis dysregulation, as well as its impact on physical and mental health and quality of life.

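### The Protocol collects a baseline for every questionnaire and HRV measure but names only unadjusted two-sample tests: valid, but less precise than a baseline-adjusted comparison

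*Protocol*

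**What the plan says.** Section 8 of the Protocol, Steps to Follow, sets two measurement times. At the start, "All participants will undergo questionnaire assessments and heart rate variability measurements before treatment". At the end, "participants will undergo a final questionnaire assessment and heart rate variability measurement after the 12th week of enrollment". Between them, participants are randomised to six weeks of CBT or six weeks of lifestyle management. The Participant subsection gives the size: "We plan to enroll a total of 120 participants".

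The Statistical Analysis subsection begins with a gatekeeping step: "All data will undergo normality testing using the Kolmogorov-Smirnov test". For continuous data it then states "Continuous variables that are normally distributed will be analyzed using the unpaired t-test", and otherwise "non-normally distributed continuous variables will be analyzed using the Mann-Whitney U test". A further sentence covers other layouts: "For comparisons involving more than three groups, if the data are normally distributed, an ANOVA with post hoc tests will be conducted", with Kruskal-Wallis as the non-normal counterpart. Significance is set at 0.05.

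The section does not mention ANCOVA, regression, a mixed model or change from baseline. It does not say whether the tests apply to week-12 values or to changes.

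**The concern.** The same scale is recorded before and after treatment in a randomised trial, so the baseline value usually predicts the final value. Using it as a covariate removes that share of the outcome variance from the comparison of arms. A two-sample test on week-12 values ignores the baseline. A test on change scores uses it with a fixed coefficient of one, which is too large unless the correlation is very high. In either case the confidence interval is wider than it need be, in a trial of 120 for which the Protocol gives no power calculation showing precision to spare.

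A narrower side point is that the normality test decides what is reported. Depending on the data, the result is either a difference in means or a rank test with medians, so the reported quantity is not fixed in advance.

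**Working it through.** The Protocol has no power figure to reproduce, so the check is of relative precision.

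**Inputs from the Protocol:** total N = 120; two randomised arms; significance level 0.05; one baseline and one week-12 assessment.

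**Assumptions not in the Protocol:** 1:1 allocation (60 per arm), two-sided test, equal SD at both times (set to 1), no dropout, approximately normal data, baseline-to-week-12 correlation r = 0.3, 0.5, 0.7 or 0.8.

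**Residual SD of each analysis**
- Week-12 value: 1
- Change score: √(2(1−r))
- ANCOVA: √(1−r²)

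**95% CI half-width** = 1.980 × √(2/60) × residual SD = 0.362 × residual SD. This needs no assumed effect.

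| r | Week-12 value | Change | ANCOVA | ANCOVA narrower than the better unadjusted choice | Unadjusted N needed to match |
|---|---|---|---|---|---|
| 0.3 | 0.362 | 0.428 | 0.345 | 1−√0.91 = 4.6% | 120/0.91 = 132 |
| 0.5 | 0.362 | 0.362 | 0.313 | 1−√0.75 = 13.4% | 120/0.75 = 160 |
| 0.7 | 0.362 | 0.280 | 0.258 | 1−√(0.51/0.60) = 7.8% | 120×0.60/0.51 = 141 |
| 0.8 | 0.362 | 0.229 | 0.217 | 1−√(0.36/0.40) = 5.1% | 120×0.40/0.36 = 133 |

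**Power for an assumed 0.5 SD effect** (noncentral t, effect divided by the residual SD)

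| r | Week-12 value | Change | ANCOVA | Gain over the better unadjusted choice |
|---|---|---|---|---|
| 0.3 | 77.5% | 63.1% | 81.3% | 4 points |
| 0.5 | 77.5% | 77.5% | 88.0% | 10 points |
| 0.7 | 77.5% | 93.9% | 96.7% | 3 points |
| 0.8 | 77.5% | 99.0% | 99.5% | 0.5 points |

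For 0.4 SD the gains are 4, 12, 6 and 2 points; for 0.6 SD they are 2, 6, 1 and 0. With 50 completers per arm and 0.5 SD they are 4, 12, 4 and 1.

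**Validity.** In simulation with normal data and 60 per arm, type I error was 4.8–5.4% for the t-test and 5.0–5.5% for ANCOVA (r = 0.3 to 0.7).

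**Skewed outcomes.** The simulation used a log-normal outcome with log-scale SD 1, a 0.5 SD effect on the log scale, and raw-scale ANCOVA with robust standard errors. The comparator is the better of Mann-Whitney on final values and Mann-Whitney on raw change. For r = 0.3, 0.5, 0.7, 0.8:
- If treatment lowers the outcome, raw-scale ANCOVA has about 17, 10, 4 and 6 points less power.
- If treatment raises it, the loss is about 16, 12, 15 and 12 points (0.743−0.585, 0.754−0.632, 0.916−0.768, 0.980−0.862).
- Power was 80.0, 86.9, 96.4 and 99.4% for log-scale ANCOVA and 77.8, 85.0, 95.2 and 98.6% for rank ANCOVA. Both exceed the better Mann-Whitney choice at every r.

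The direction matters because Mann-Whitney on raw change is weaker when the outcome falls (power about 44, 60, 80 and 93%) than when it rises.

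**The case against.** The strongest reply is that nothing here is an error. The tests are valid under randomisation, and the Statistical Analysis text is generic: it is not tied to week 12 or to an outcome, and would serve equally for a baseline table. Covariate adjustment is often left to a statistical analysis plan, which is not shown and could specify it. Part of this stands. Reading the text as the two-arm comparison is an inference, although two arms and a separate sentence for larger numbers of groups make it the natural one. But the Protocol is not silent on method: it names the tests and the rule for choosing between them. The point is about that stated choice.

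It is also fair that the gain is modest and peaks near r = 0.5. A reader might infer a much larger loss at r = 0.7 by comparing ANCOVA only with week-12 values: 120/0.51 = 235 participants to match. The Protocol does not exclude change scores, and against those the figure is 141.

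Three stronger readings are not supported. The unadjusted tests are not biased and do not inflate type I error. No type I error inflation has been shown from the Kolmogorov-Smirnov selection either. And the gain is not entirely free, because the remedy can lose power if the scale is badly chosen. The Mann-Whitney fallback already gives some protection against skew.

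**Conclusion.** The point holds as one of efficiency only. On the natural reading, the named tests are valid but less precise than a baseline-adjusted comparison. With 60 per arm, two-sided 0.05 and near-normal data, the interval would be about 5–13% narrower than under the better unadjusted choice for r between 0.3 and 0.8. Power at 0.5 SD would rise by 0.5 to 10 points. If the worse quantity were tested, the difference is larger: 78% against 97% at r = 0.7 for week-12 values, and 63% against 81% at r = 0.3 for change scores. Since the Protocol gives neither the quantity nor the correlation, ANCOVA also removes that gamble.

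The allocation ratio, sidedness, correlation, effect size and completeness of follow-up are assumptions. The arithmetic is firm; its application depends on reading the section as the between-arm comparison and on no separate plan already adjusting for baseline. The change is worth making, but the planned analysis would not be wrong without it.

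**What to change.** In the Protocol's Statistical Analysis section:

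- State that the between-arm comparison of each continuous outcome at week 12 is an ANCOVA on arm and that outcome's own baseline, reporting the adjusted difference and its 95% CI.
- Name in advance a log-scale or rank-based ANCOVA for outcomes expected to be strongly skewed, such as HRV indices.
- Use the Kolmogorov-Smirnov test only to choose how descriptive tables are presented.
- Keep the Mann-Whitney test as a sensitivity analysis.
- If a separate analysis plan already specifies an adjusted model, bring the Protocol text into line with it.

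No new data, visits or participants are needed. The cost is some drafting and one real decision: the raw, log or rank scale must be fixed for each outcome before unblinding. The list of instruments is long, and the Protocol offers no distributional data to guide the choice.
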